#### 5.1.2. Secondary effectiveness endpoint and secondary analyses

Secondary effectiveness endpoints are the incidence of “cardiogenic cerebral embolism” or “cerebral infarction” or “hemorrhagic stroke” during the follow-up period. in NVAF patients treated with warfarin or apixaban.

1. Incidence rate (per 1,000 person-years) of recurrent “cardiogenic cerebral embolism” during the follow-up period in NVAF patients treated with warfarin or apixaban.
2. Time course of proportion of the incidence of recurrent “cardiogenic cerebral embolism”-free NVAF patients treated with warfarin or apixaban (shown as two Kaplan-Meier curves, for warfarin cohort and apixaban cohort, which will be statistically compared by a Log-rank test).
3. Risk of recurrent “cardiogenic cerebral embolism” in patients treated with apixaban compared to that in patients treated with warfarin. Hazard ratio and 95% confident intervals will be calculated by a COX proportional hazard method.

PFIZER CONFIDENTIAL

4. Incidence rate (per 1,000 person-years) of recurrent "**cerebral infarction**" during the follow-up period in NVAF patients treated with warfarin or apixaban.
5. Time course of proportion of the incidence of recurrent "**cerebral infarction**"-free NVAF patients treated with warfarin or apixaban (shown as two Kaplan-Meier curves, for warfarin cohort and apixaban cohort, which will be statistically compared by a Log-rank test).
6. Risk of recurrent "**cerebral infarction**" in patients treated with apixaban compared to that in patients treated with warfarin. Hazard ratio and 95% confident intervals will be calculated by a COX proportional hazard method.

## 5.2. SAFETY ENDPOINTS

### 5.2.1. Primary safety endpoint and primary analyses

The following outcomes will be assessed as safety endpoints. The primary safety endpoint is **major bleeding**, which is defined as any bleeding requiring hospitalization for treatment (the primary reason for the hospitalization is to treat the bleeding). Because "hospitalization" is a requirement, only outpatients will be included in the analysis and patients who are already hospitalized at the time of bleeding (bleeding during hospitalization) will be excluded from the analysis.

1. Incidence rate (per 1,000 person-year) of **major bleeding** during the follow-up period in NVAF patients treated with warfarin or apixaban.
2. Time course of proportion of **major bleeding**-free in NVAF patients treated with warfarin or apixaban (shown as two Kaplan-Meier curves, for warfarin cohort and apixaban cohort, which will be statistically compared by a Log-rank test).
3. Risk of **major bleeding** in NVAF patients treated with apixaban compared to that in patients treated with warfarin. Hazard ratio and 95% confident intervals will be calculated by a COX proportional hazard method.

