8.1.1.1. Index date

The next day of the day when patients diagnosed NVAF initiate warfarin or apixaban

8.1.1.2. stroke

8.1.1.3. Defined using pre-designated ICD-10 codes (see Statistical Analysis Plan). Ischemic and hemorrhagic stroke will be included,stroke

Stroke is defined using predefined ICD-10 codes and if hospitalization for the treatment of the stroke is necessary, it will be regarded as stroke incident during the followup period.
(applicable only to the outpatients when recurrent stroke occurs)

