8.1.1.4. Major bleeding

Major bleeding is defined any bleeding that needs hospitalization for the treatment of bleeding. Any bleeding is defined using pre-designated ICD-10 codes (see Statistical Analysis Plan).

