#### **4.2. SAFETY ANALYSIS SET**

Bleeding other than safety-related reactions will not be investigated here. Bleeding events will be evaluated using the same analysis set as effectiveness.

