#### **4.3. OTHER ANALYSIS SET**

Not applicable. All eligible patients will be used for the analysis except the pre-designated sub-analysis.

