## 5. ENDPOINTS AND COVARIATES

### 5.1. EFFICACY/EFFECTIVENESS ENDPOINT(S)

#### 5.1.1. Primary effectiveness endpoint and primary analyses

The following outcomes will be assessed as effectiveness endpoints. Primary endpoint is incidence of a composite of recurrent stroke (ischemic and hemorrhagic stroke)/SE in NVAF patients treated with warfarin or apixaban. The definition of “recurrent” is as follows, “once patients discharge from the hospital and become outpatients and then rehospitalized due to stroke (major reason for the hospitalization is stroke described in the DPC admission information)

[figure not shown]
[figure not shown]
1. Incidence rate (per 1,000 person-years) of a composite of recurrent stroke (ischemic and hemorrhagic stroke)/SE during the follow-up period in NVAF patients treated with warfarin or apixaban
2. Time course of proportion of the incidence of a composite of recurrent stroke (ischemic and hemorrhagic stroke)/SE-free NVAF patients treated with warfarin or apixaban (shown as two Kaplan-Meier curves, for warfarin cohort and apixaban cohort, which will be statistically compared by a Log-rank test).
3. Risk of a composite of recurrent stroke (ischemic and hemorrhagic stroke)/SE in patients treated with apixaban compared to that in patients treated with warfarin. Hazard ratio and 95% confident intervals will be calculated by a COX proportional hazard method

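### As worded, SAP 5.2.1 deletes patients who bleed in hospital after index from the primary safety analysis, against SAP 4.2 and 4.3; the sentence should be an event rule

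*SAP*

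**What the plan says.** SAP 5.2.1 makes major bleeding the primary safety endpoint and requires the bleed to be the main reason for an admission. It gives that requirement as the reason for two rules. The first is that "only outpatients will be included in the analysis"; when outpatient status is judged is left open. The second rule deals with bleeds that occur in hospital: "patients who are already hospitalized at the time of bleeding (bleeding during hospitalization) will be excluded from the analysis".

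Other sections describe a different set. SAP 4.2: "Bleeding events will be evaluated using the same analysis set as effectiveness". SAP 4.3: "All eligible patients will be used for the analysis except the pre-designated sub-analysis". SAP 4.4 lists no subgroups, and Protocol 8.1.1.4 defines major bleeding without excluding any patient.

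On timing, Protocol 8.1.1.1 sets the index date at "The next day of the day when patients diagnosed NVAF initiate warfarin or apixaban", whatever the hospital status. SAP 5.1.1 counts a stroke as recurrent "once patients discharge from the hospital and become outpatients and then rehospitalized due to stroke", and Protocol 8.1.1.3 marks its stroke rule as "applicable only to the outpatients when recurrent stroke occurs". The five ends of follow-up in Protocol 8.1.1.7 are discontinuation, switch, last record, stroke or major bleeding, and two years. None starts the clock at discharge or takes out inpatient days.

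SAP exclusion 5 removes only stays of more than 6 months that include the index date. Protocol exclusion 5 removes patients continuously in hospital for a first stroke or another serious disease, and gives no duration.

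**The concern.** An exclusion triggered by a bleed during follow-up makes membership of the safety set depend on the patient's own later outcome, and on an outcome closely related to the endpoint. If bleeding in hospital and bleeding at home share causes, the people removed are those more likely to have had a primary event, and the arms may lose different numbers. The sentence can also be read in more than one way, so two programmers working from 5.2.1, 4.2 and 4.3 could build different primary safety sets.

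The second issue is time at risk. If patients start the drug during an admission and enter the cohort, their remaining inpatient days go into the denominator although neither a major bleed nor a recurrent stroke can be counted in them. Incidence rates are named outputs for both primary endpoints, so dilution matters for the rates even if the hazard ratio is little affected.

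**Working it through.** **1. Who is in the set.** The plan gives no figure for this point, so the check is a comparison of texts. SAP 7.2.2 reports more than 15,000 secondary prevention patients; 15,000 is used as illustration.

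| Reading of 5.2.1 | Consistent with 4.2/4.3? | Patients analysed |
|---|---|---|
| In-hospital bleeds are not events | Yes | 15,000 |
| Patients who bleed in hospital are deleted | No | 14,130 to 14,970 |
| Patients in hospital at index are deleted | No | 7,500 to 12,000 |

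Row 2 assumes 0.2% to 5.8% are removed, from a simulation with assumed inputs: 15,000 × 0.002 = 30 and 15,000 × 0.058 = 870. Row 3 assumes 20% to 50% are inpatients at index.

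The follow-up list does not choose between the readings. If the event reading is adopted, though, the list is sufficient. An in-hospital bleed does not meet the 5.2.1 definition, so item 4 of Protocol 8.1.1.7 is not triggered and follow-up runs on.

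**2. Delete, censor or continue.** Simulation inputs, all assumed:
- true outpatient rate ratio 0.70
- 1.0 in-hospital bleeds per inpatient-year, with an in-hospital ratio of 0.4
- 50% inpatient for 30 days at index
- gamma frailty on bleeding and admission

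| Frailty variance | Continue | Delete | Censor at the bleed |
|---|---|---|---|
| 1 | 0.707 | 0.726 | 0.730 |
| 3 | 0.708 | 0.761 | 0.766 |

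Repeat runs moved the levels by about 0.01 and left the order unchanged. Continued follow-up stays near 0.70, and censoring is no better than deletion. These are deliberately strong inputs. With 0.1 to 0.3 in-hospital bleeds per inpatient-year and frailty variance up to 1, the three differ by less than 0.01. If the in-hospital ratio is above 0.70 (1.2 was tried), the shift reverses sign.

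**3. Person-time in which nothing can count.** Inputs: the 730-day cap (Protocol 8.1.1.7); the inpatient share p, remaining stay L and mean follow-up F are not in the documents and are assumed. With exponential retention at rate λ per day, the mean time observed up to day L is A(L) = (1 − exp(−λL))/λ, with λ set so that A(730) = F. The rate is too low by the share p × A(L)/F.

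For F = 365, λ = 0.002183, A(14) = 13.79 and A(30) = 29.04 days:
- p = 20%, L = 14: 0.20 × 13.79/365 = 0.76%
- p = 30%, L = 14: 0.30 × 13.79/365 = 1.13%
- p = 30%, L = 30: 0.30 × 29.04/365 = 2.39%
- p = 50%, L = 30: 0.50 × 29.04/365 = 3.98%

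For F = 730 (no drop-out, A(L) = L) the four values are 0.38%, 0.58%, 1.23% and 2.05%. A long-stay case, p = 50% and L = 90, gives 11.19% at F = 365. If no inpatients enter, the loss at index is zero. Later admissions create the same kind of time and are not included here.

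**4. Hazard ratio.** Taking the planning value 0.65 from SAP 7.2.2 (a stroke/SE value) and F = 365, the apparent ratio is about 0.65 × (1 − loss in apixaban)/(1 − loss in warfarin).
- Equal inpatient time: 0.65.
- p = 30%: 0.654 with 14 warfarin and 7 apixaban days left; 0.646 with these reversed.
- p = 50%: 0.676 with 60 warfarin and 30 apixaban days left; 0.625 with these reversed.

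**5. Kaplan-Meier.** At the stroke/SE planning rates of 1.2% to 2.6% per year and without drop-out, cumulative incidence is too low by 0.01 to 0.03 percentage points (20% to 30% inpatients, 14 days) or 0.05 to 0.11 points (50%, 30 days), about the same at day 30 and at two years.

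**The case against.** The strongest reply is that 5.2.1 was only ever an event rule. It justifies itself by the admission requirement, SAP 5.2.2 gives the mirror rule for secondary bleeding endpoints (hospital status is irrelevant there), and Protocol 8.1.1.3 restricts stroke in the same way. This is probably the intention. It does not rescue the sentence, which names patients and the analysis, and which a programmer may follow literally.

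The reply to the person-time point is also substantial. Two figures in SAP 5.1.1 are not shown and may deal with the start of risk time. Protocol exclusion 5 might remove most index inpatients. If the outpatient clause is applied at index, those patients leave the bleeding analysis and the point survives only for stroke. The text does not say whether SE needs readmission. Admissions for bleeding per on-treatment person-year is itself a legitimate measure. The propensity score includes treatment status and length of stay for the most recent stroke (SAP 7.1.2), which lessens any imbalance, although it does not include inpatient status or remaining stay at index. All of this stands, and it is why the point supports a sensitivity analysis and no change of the main analysis.

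A reader might also infer that patients should be censored at an in-hospital bleed. That would add an end of follow-up absent from Protocol 8.1.1.7, and step 2 shows it does no better than deletion.

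**Conclusion.** The main point holds on the wording: 5.2.1 as written selects on a post-index bleed and contradicts SAP 4.2 and 4.3. It should be fixed whichever meaning was intended. This part needs no assumed figures.

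The person-time point is secondary and conditional. If index inpatients enter, rates are too low by about 1% to 4% for 20% to 50% inpatients with 14 to 30 days left and a mean follow-up of 365 days, all assumed. The hazard ratio probably changes little.

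A reader might infer that the primary safety hazard ratio is materially biased, or biased towards apixaban. The documents do not support this. They give no inpatient share, remaining stay, in-hospital bleeding rate or difference between arms, and the direction changes with which arm has more inpatient time or more in-hospital bleeds. Nor do they show that deletion was intended.

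**What to change.** (a) Replace the 5.2.1 exclusion with wording to this effect: All eligible patients remain in the analysis set (4.2/4.3). A bleed that occurs during a hospitalization is not a primary safety event; the patient is neither deleted nor censored at that bleed, and follow-up continues under Protocol 8.1.1.7.

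(b) Report in-hospital bleeds by arm, and add a supportive analysis that counts them as events using the any-bleeding code list to which Protocol 8.1.1.4 refers. This is a different endpoint and does not test for informative censoring.

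(c) Keep the index-date start as the main analysis. For both primary endpoints, add a sensitivity analysis that starts time at risk at the later of the index date and discharge from the initiation admission. Report inpatient share and remaining stay at index by arm after weighting.

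(d) Reconcile Protocol exclusion 5 with SAP exclusion 5, using only information known at index. The SAP version can depend on days in hospital after index.

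The cost is a few sentences and some reruns on the same data. The discharge-start analysis loses early person-time and conditions on reaching discharge event-free and still on drug, which is why it should stay a sensitivity analysis.

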### 5.2.2. Secondary safety endpoint and secondary analyses

Secondary safety endpoints are intracranial hemorrhage, gastrointestinal bleeding or intraocular bleeding during the follow-up period. Because hospitalization is not used for the definitions of these secondary endpoints, It does not matter whether the patient is hospitalized or visiting a hospital as outpatients when these endpoints occur.

1. Incidence rate (per 1,000 person-year) of intracranial hemorrhage during the follow-up period in NVAF patients treated with warfarin or apixaban.
2. Time course of proportion of intracranial hemorrhage-free in NVAF patients treated with warfarin or apixaban (shown as two Kaplan-Meier curves, for warfarin cohort and apixaban cohort, which will be statistically compared by a Log-rank test).
3. Risk of intracranial hemorrhage in NVAF patients treated with apixaban compared to that in patients treated with warfarin. Hazard ratio and 95% confident intervals will be calculated by a COX proportional hazard method.
4. Incidence rate (per 1,000 person-year) of gastrointestinal bleeding during the follow-up period in NVAF patients treated with warfarin or apixaban.
5. Time course of proportion of gastrointestinal bleeding-free in NVAF patients treated with warfarin or apixaban (shown as two Kaplan-Meier curves, for warfarin cohort and apixaban cohort, which will be statistically compared by a Log-rank test).
6. Risk of gastrointestinal bleeding in NVAF patients treated with apixaban compared to that in patients treated with warfarin. Hazard ratio and 95% confident intervals will be calculated by a COX proportional hazard method.
7. Incidence rate (per 1,000 person-year) of intraocular bleeding during the follow-up period in NVAF patients treated with warfarin or apixaban.
8. Time course of proportion of intraocular bleeding-free in NVAF patients treated with warfarin or apixaban (shown as two Kaplan-Meier curves, for warfarin cohort and apixaban cohort, which will be statistically compared by a Log-rank test).
9. Risk of intraocular bleeding in NVAF patients treated with apixaban compared to that in patients treated with warfarin. Hazard ratio and 95% confident intervals will be calculated by a COX proportional hazard method.

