### 4. ANALYSIS SETS/POPULATIONS

#### 4.1. FULL ANALYSIS SET

##### 4.1.1. Inclusion criteria

*Patients must meet all the following selection criteria*

1. *Patients registered in the MDV database 2008 through 2021.*
2. *Patients newly diagnosed with non-valvular atrial fibrillation*
3. *Patients who started anticoagulation treatment with either warfarin or apixaban after diagnosis of NVAF*
4. *Age 20 years or older on the index date*
5. *Patients who have a history\* of stroke (cerebral infarction, cardioembolic stroke, or hemorrhagic stroke) or TIA before the index date are inclusion criteria only for secondary prevention cohort, otherwise patients will be included in the primary prevention cohort.*

\* A history of stroke is checked as far back as possible from the INDEX DATE to see if there is a history of stroke. That is, the period is from the date each patient first appeared in the MDV database to the day before the index date.

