Ischemic stroke (1)+(2)	Outcome	Defined elsewhere using ICD-10 codes
(1) Cardiogenic cerebral embolism	Outcome	Defined elsewhere using ICD-10 codes
(2) Cerebral infarction	Outcome	Defined elsewhere using ICD-10 codes
Hemorrhagic stroke	Outcome	Defined elsewhere using ICD-10 codes
Systemic embolism	Outcome	Defined elsewhere using ICD-10 codes
Bleeding	Outcome	
Major bleeding (Any bleeding requiring hospitalization)	Outcome	Refer to excel sheet in section 10.3
Intracranial hemorrhage	Outcome	Defined elsewhere using ICD-10 codes
Gastrointestinal tract bleeding	Outcome	Defined elsewhere using ICD-10 codes
Intraocular bleeding	Outcome	Defined elsewhere using ICD-10 codes

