**9.3. APPENDIX 3: DIAGNOSIS AND PROCEDURE CODES USED IN THE STUDY**

The list of ICD-10 codes is shown in following excel sheet.

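### Intracranial hemorrhage (SAP 5.2.2) has no incident-event rule in a cohort that admits prior hemorrhagic stroke, so diagnoses continuing from the qualifying bleed can be counted as new events

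*SAP*

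**What the plan says.** **Who enters.** SAP 4.1.1 defines the secondary prevention cohort by a history of "cerebral infarction, cardioembolic stroke, or hemorrhagic stroke) or TIA before the index date". The history is searched through all of the patient's earlier database records, and no minimum gap is set between the old stroke and index. SAP 4.1.2, exclusion 5, removes patients for a long hospital stay spanning index only if it exceeds 6 months. Protocol 8.2.2, exclusion 5, is worded differently: it removes patients continuously hospitalized for a first stroke or other serious disease.

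**How ICH is counted.** SAP 5.2.2: "Secondary safety endpoints are intracranial hemorrhage, gastrointestinal bleeding or intraocular bleeding during the follow-up period". It continues: "Because hospitalization is not used for the definitions of these secondary endpoints", and "It does not matter whether the patient is hospitalized or visiting a hospital as outpatients when these endpoints occur". The outcome table in SAP 5.4 gives the operational definition as "Defined elsewhere using ICD-10 codes". Appendix 3 says only: "The list of ICD-10 codes is shown in following excel sheet". That sheet is not reproduced, and Appendix 1 on data derivation is marked not applicable.

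**How the primary endpoints are counted.** SAP 5.1.1 defines recurrent stroke as occurring "once patients discharge from the hospital and become outpatients and then rehospitalized due to stroke". SAP 5.2.1 requires that treating the bleed be the main reason for admission, and leaves out bleeds in patients already in hospital.

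**What is adjusted or tested.** The propensity score in SAP 7.1.2 includes the type of the most recent stroke (with cerebral bleeding as a category) and bleeding history. Balance is accepted at a standardized difference of 0.1. SAP 7.2 treats secondary endpoints as exploratory.

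**The concern.** A patient who qualified through a hemorrhagic stroke may still carry that diagnosis at a visit after index, or may be in hospital for it on the index date. Under 5.2.2 as written, either record can meet the ICH endpoint. The same kind of event is screened in 5.1.1 by discharge and readmission, and in 5.2.1 by the reason for admission; 5.2.2 drops the screen and puts nothing in its place.

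The SAP commits to an incidence rate, a Kaplan-Meier curve with log-rank test, and a hazard ratio for ICH. Carried-over diagnoses would raise the rate in both arms, steepen the curve soon after index, and distort the ratio. Nothing planned would show this: SAP 4.4 lists no subgroups, and the only sensitivity analysis (7.2.1) is an E-value for the primary analyses, which addresses unmeasured confounding and not misclassified outcomes.

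Gastrointestinal and intraocular bleeding share the any-setting definition. ICH is the most exposed because prior hemorrhagic stroke is itself a route into the cohort.

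**Working it through.** The plan gives no ICH rate, no share of patients with prior hemorrhage and no carry-over frequency. The table in SAP 7.2.2 concerns stroke/SE, so there is no ICH figure to reproduce.

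**Step 1. Rules side by side.**

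| Endpoint | New admission needed? | In-hospital events counted? | Rule separating a new event from an old one |
|---|---|---|---|
| Stroke, as recurrent (5.1.1) | Yes, after discharge | No | Discharge, then readmission for stroke |
| Major bleeding (5.2.1) | Yes, for the bleed | No | Reason for admission |
| ICH (5.2.2) | No | Yes | None stated |

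**Step 2. Equal carry-over in both arms.** All inputs are assumptions:
- true ICH rate 10 (warfarin) and 5 (apixaban) per 1,000 person-years, a ratio of 0.5;
- *k* carried-over events per 1,000 patients. Low case: 5% with prior hemorrhage × 10% re-coded = 5. High case: 10% × 30% = 30;
- history and outcome code lists overlap.

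Over *T* years, apparent ratio = (5*T* + *k*)/(10*T* + *k*).

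| | *k* = 5 | *k* = 30 |
|---|---|---|
| *T* = 1 | 10/15 = 0.67 | 35/40 = 0.875 |
| *T* = 2, carry-over counted once | 15/25 = 0.60 | 40/50 = 0.80 |

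Two years is the maximum follow-up (Protocol 8.1.1.7). The warfarin event count is inflated 1.5- to 4-fold over 1 year (15 or 40 instead of 10) and 1.25- to 2.5-fold over 2 years (25 or 50 instead of 20).

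**Step 3. Unequal carry-over.** With *k*w and *k*a for warfarin and apixaban, the apparent ratio is (5*T* + *k*a)/(10*T* + *k*w). This is a weighted mean of the true ratio (weight 10*T*) and *k*a/*k*w (weight *k*w). The pull is towards 1 when *k*a = *k*w. It is below the true ratio when *k*a/*k*w is smaller than that ratio, and the result can pass 1 when *k*a/*k*w exceeds 1.

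Now allow the largest imbalance that the plan accepts, using d = (p1 − p0)/√{[p1(1 − p1) + p0(1 − p0)]/2}. With p0 = 10% on warfarin, d = ±0.1 gives p1 = 13.2% or 7.2% on apixaban. At 30% re-coded, *k*w = 30 and *k*a = 39.6 or 21.6. Over 2 years:
- 13.2% on apixaban: (10 + 39.6)/(20 + 30) = 0.99;
- 7.2% on apixaban: (10 + 21.6)/(20 + 30) = 0.63.

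With equal shares the value is 0.80. A harsher case shows both directions: true ratio 0.65 (borrowed from the stroke/SE assumption in SAP 7.2.2), 5% prior hemorrhage on warfarin, 50% re-coded, so *k*w = 25. Apixaban at 7.4% or 3.0% (d of about ±0.1) gives *k*a = 37 or 15:
- 7.4%: (13 + 37)/(20 + 25) = 1.11;
- 3.0%: (13 + 15)/(20 + 25) = 0.62, slightly below the true 0.65.

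**The case against.** The strongest reply is that the text does not say every code counts. Section 5.2.2 speaks of incidence during follow-up and of endpoints occurring, which is the language of onset. Nothing in the documents shows that old ICH codes recur in this database or that the history and outcome code lists overlap, and the unseen sheet may leave out sequela or chronic codes. This stands as a limit: a reader might infer that old bleeds will be counted, and the documents show only that the stated rule does not prevent it. It does not close the gap, because a list of codes does not supply a look-back or new-onset rule.

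A reader might also infer a fixed bias towards 1, or that most counted ICH is spurious. Neither is supported. The direction depends on balance, as step 3 shows, and any false share merely restates the assumed inputs. More extreme ratios need more imbalance than the plan accepts: prior hemorrhage of 15% against 10%, for example, is a standardized difference of about 0.15. The score also contains stroke type and bleeding history, so rough balance is plausible. It is not assured, since only the most recent stroke is used and an older hemorrhage followed by an ischemic stroke does not appear under stroke type.

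It is also fair that counting in-hospital ICH looks deliberate, and that Protocol 7.1 names recurrent bleeding as a safety objective. An admission-only rule would lose the former, and a first-ever-code rule alone would lose true recurrences. The fix has to respect both.

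Finally, the endpoint is exploratory. That limits the consequence, but exploratory status answers multiplicity and does not cure a definition that may count old disease; the absolute rate would be inflated even with perfect balance.

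**Conclusion.** The concern holds in a limited form. As written, SAP 5.2.2 allows diagnoses continuing from the qualifying bleed to be counted as new ICH, through follow-up codes or through an admission already under way at index. The second route exists under SAP exclusion 5; the differently worded protocol exclusion would narrow it, and the two need reconciling.

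The expected effects are an inflated ICH rate and early Kaplan-Meier drop and, if carry-over is equal between arms, a hazard ratio biased towards 1. If prior hemorrhage is not balanced, the direction is uncertain, even within the plan's tolerance. The size cannot be derived from the documents. The ranges of 0.67 to 0.875 (1 year) and 0.60 to 0.80 (2 years) for a true 0.5 are illustrations resting wholly on the assumptions in step 2.

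The matter is worth correcting but does not threaten the study's main results: both primary endpoints carry admission rules, and their conclusions are unaffected.

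**What to change.** In SAP 5.2.2, count ICH as an event only if it is one of the following:
- (a) in a patient with no earlier ICH code in any available record, a first ICH code after index, in any setting;
- (b) in a patient with an earlier ICH code, either a new admission with ICH as the main or admission-triggering diagnosis, or an ICH coded as arising after admission during a stay that was not for the earlier bleed.

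Do not count codes from an admission already under way at index for the qualifying bleed. Confirm that the extract distinguishes diagnoses arising after admission, since the documents do not say. State which version of exclusion 5 applies.

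Add a sensitivity analysis for ICH that excludes patients with any ICH code before index. For gastrointestinal and intraocular bleeding, leave true recurrences in the main analysis and add a sensitivity analysis excluding patients with the same code in the look-back.

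The cost is SAP wording, one programming rule and a few extra outputs, with no new data collection. The downside is that a few recurrent ICH cases managed without a new admission will be missed.
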